9.2 Observations by Visit

Visits and assessments should occur within the schedule in Table 2 according to study. All times should be recorded using the 24-hour clock (e.g., 23:20, not 11:20 pm).

9.2.2 Screening

- If patient has had an appt with a physical exam in the last 30 days, that can be used for this screen.
- Obtain written informed consent.
- Verify inclusion and exclusion criteria
- Demographics and medical history
- MS Scoring and History
- Pregnancy test (for women of child-bearing potential patients only), whether to be done on urine or blood will be at investigator's discretion or per institutional practice.
- Collect blood sample for laboratory assessment (Table 1) (note: samples will be sent to local laboratories)
- Record pre-study/concomitant medication
- Randomization 1:1

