9. STUDY CONDUCT

9.1 Schedule of Assessments

The schedule of assessments is shown in months, as it facilitates better comprehension, preventing potential errors, in the interpretation of the exact timing for each assessment. On the other hand, in order to facilitate integration with the weekly-based schedule of ECP, and also budget considerations, we use the following transformation between weeks and months when addressing the schedule of assessments:

- a- 3 months: Week 12 \pm 2 week
- b- 6 months: Week 24 \pm 2week
- c- 9 months: Week 36 \pm 2 week
- d- 12 months or 1 year: Week 52 \pm 1 month

The schedule of assessments is shown in Table 2.

Table 2: Schedule of Assessments

Procedures	Screening (-30days)	Baseline ⁵ (Week 2)	Month 3	Month 6	Month 9	12 months/1year	Til End of Study (every 3 months through 2 years) ⁸
Informed Consent	X						
Inclusion/Exclusion Criteria	X						
Vital Signs		X	X	X	X	X	
Medical History/ Interim History ¹	X	X	X	X	X	X	
Physical Examination		X	X	X	X	X	
MSFC ⁸		X	X	X	X	X	X
EDSS ⁸		X	X	X	X	X	X
MRI		X		X		X	
Pregnancy Test ²	X						
Immune Parameters Measurement		X	X	X	X	X	
Clinical Laboratory Tests ³	X	X				X	
Pre-study/Concomitant MedicationsMRI	X	XX	X	XX	X	XX	
Adverse Events	X	X	X	X	X	X	
Randomization to ECP ^{5,6} vs IVMP ⁷	X						

¹ Including history of MS, progression from RRMS to onset of SPMS. A complete history at start of study and interim history at each visit.

²For women of childbearing potential.

³ Both at screening and prior to each ECP procedure, a small amount of blood (2-4 teaspoons) will be drawn to evaluate CBC and chemistries.

⁴Subjects will be randomized at a 1:1 ratio to either ECP.or IVMP

⁵Patients should have ECP within 14 days of baseline visit.

⁶The frequency of ECP treatments will be:

Weeks 1-8: 3 x/ week

Weeks 9-16: 2x/week

Weeks 17-36: 2x/2 weeks

Weeks 37-43: 1x / every 2 weeks

Weeks 44-52: 1x/ every 4 Weeks

⁷ Corticosteroid is administered on a pulse basis and consists of 1 gram of methylprednisolone I.V. every 4 Weeks for 52 Weeks.

⁸These test will occur every three month through 2 years.

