9.2.3 Baseline (Week 1)

A baseline visit should be performed and 1st ECP scheduled within 14days.

- Physical examination.
- Interim History
- Vital signs.
- MSFC
- MRI
- EDSS
- Blood for immune parameters (sent to the University of Michigan Neuroimmunology Research Laboratory)
- Collect blood sample for laboratory assessment (Table 1)
- Record concomitant medication.
- Assessment of pre-treatment events (AEs occurring from ICF signed to baseline visit).
- Start ECP within 14 days of baseline as defined in the schedule of assessments

9.2.4 Month 3/Week 12

- At this point patients who are assigned to ECP arm will have been tapered from 3 treatments weekly to two treatments weekly.
- Patients randomized to the ECP arm must receive their first ECP treatment within 14 days of baseline visit.
- Before ECP, on each day of treatment, blood samples will be collected for CBC or other clinical routine testing as needed, and no less that weekly.
- Patients admitted to the corticosteroid arm will receive a treatment once every month as stated above

- The following will also be performed at this time point: Interim history, vital signs, physical exam.
- Blood for immune parameters (sent to the UM Neuroimmunology Research Laboratory)
- MSFC
- EDSS
- Adverse Events
- Concomitant Medications

9.2.5 Month 6/Week 24

At this point patients on ECP will have been tapered to two treatments (on 2 consecutive days) every 2 weeks. If preferred, patients may be given the option of receiving one weekly treatment (as opposed to two treatments on 2 consecutive days) a schedule modification

- Before ECP on each day of treatment blood samples will be collected for the laboratory tests on Table 1 and sent to the University of Michigan Clinical Laboratory
- Patients admitted to the corticosteroid arm will receive a treatment once every month as stated above
- The following will also be performed at this time point:
 - Interim history, vital signs, physical exam.
 - Blood for immune parameters (sent to the UM Neuroimmunology Research Laboratory)
 - MSFC
 - EDSS
 - Adverse Events
 - Concomitant Medications
 - MRI with Gadolinium

9.2.6 Month 9/Week 36

On weeks 37-43, ECP-treated patients transition to one treatment every two weeks and for Patients admitted to the corticosteroid arm will receive a treatment once every month

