10.1 Planned Sample Size and Number of Study Centers

It is planned to recruit approximately 66 patients (33 per treatment arm). This is a single center study.

Patients will be randomized on a 1:1 basis to corticosteroids or ECP arm.

Patients randomized to the ECP treatment arm must receive their first treatment within 5 days of the baseline visit.

For the randomization of patients, the investigator will use an Interactive Voice Response System (IVRS). Details can be found in the trial master file. IVRS will assign patients to a treatment group based on the pre-defined randomization list.

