10.2 Efficacy Analyses

10.2.1 Analysis of Primary Endpoint

The primary end point is the proportion of subjects with no evidence of disease progression, as defined below, at Week 52. Intent to treat approach will be used. Progression is defined as a minimum change from baseline in one or more of the following parameters:

- 20% or greater increase in the timed 25 foot walk
- 20% or greater increase in the 9 hole peg test
- 1 point or greater increase in EDSS score in subjects with baseline EDSS scores between 3 and 5.5
- 0.5 point or greater increase in EDSS score in subjects with baseline EDSS scores equal to or greater than 6

The proportion of subjects who have not progressed clinically, based on the above criteria, at Week 52 after initiation of study therapy will be compared between treatment groups using the Chi-square test.

The early drop-outs, including patients who withdraw will be considered as non-responders.

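### Randomisation is scheduled at screening, before the baseline timed walk, peg test and EDSS, so the endpoint's reference values can be recorded with the arm known

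*Combined protocol and SAP*

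**What the plan says.** - **Randomisation.** Section 9.2.2 (Screening) closes its list with "Randomization 1:1". In Table 2 (Section 9.1) the row beginning "Randomization to ECP" has one mark, in the screening column, which allows up to 30 days. Section 11.9 gives screening up to 1 week.
- **Baseline measures.** Table 2 first marks the MSFC and EDSS in the baseline column. Section 9.2.3 lists both at that visit and says: "A baseline visit should be performed and 1st ECP scheduled within 14days". The timed 25-foot walk and 9-hole peg test are MSFC components (8.1.1).
- **Scoring at screening.** Section 9.2.2 lists "MS Scoring and History" without defining it. Inclusion criterion 2 requires an EDSS of 3 to 6.5 at screening.
- **Release of the assignment.** Section 10.1 says "IVRS will assign patients to a treatment group based on the pre-defined randomization list" and, on further detail, "Details can be found in the trial master file". It says nothing about when the arm becomes known relative to baseline.
- **Endpoint.** Section 10.2.1: "Progression is defined as a minimum change from baseline in one or more of the following parameters". The criteria are a 20% rise in walk time, a 20% rise in peg-test time, and an EDSS rise of 1 or 0.5 point depending on the starting score.
- **Masking.** The trial is open-label (3.1). Section 8.1.2 has one neurologist rate the EDSS and does not say that this rater is unaware of the arm.

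**The concern.** Randomisation makes the arms comparable on whatever is measured before the assignment is known. It does not protect a reference value recorded afterwards. Here that value is the denominator of the two timed-test criteria and the starting point of the EDSS criteria. A slower walk or peg time, or a worse EDSS, recorded at baseline in one arm makes it easier for that arm to finish without progression, whatever the treatment does.

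The timed tests depend on patient effort, and a patient who already knows the assignment may perform differently. The fixed test order and same-room rule in 8.1.1, and the rater guidance in Appendix 2, limit discretion but do not conceal the arm. Open-label bias at Week 52 exists in any case. This is a second source, at the one assessment that can be protected without blinding treatment.

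**Working it through.** **1. Order of events.** Table 2 and 9.2.2 agree that randomisation belongs to screening. Table 2 and 9.2.3 agree that the MSFC and scheduled EDSS belong to baseline. Only maximum gaps are stated (30 days; 1 week). No minimum is given, and same-day visits are not barred.

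**2. The plan's own figure.** Section 10.4 assumes 30% v 60% without progression, 33 per arm, one-sided 5%. With the pooled normal approximation:

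z = [0.30 − 1.645·√(2·0.45·0.55/33)] / √((0.30·0.70 + 0.60·0.40)/33) = 0.844, so power = 0.8006.

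This reproduces the stated figure of at least 80%, with almost no margin. Exact binomial enumeration of the uncorrected chi-square (z) test gives power 0.8122, and a false-positive rate of 0.0518 at 30% v 30%.

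**3. Effect on one threshold.** If a baseline time is recorded 5% slow, a patient must truly slow by 1.20 × 1.05 − 1 = 26.0% to count as progressed. At 2% the figure is 22.4%, and at 10% it is 32.0%.

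**4. Effect on the composite.** The assumptions below are not from the documents, and the direction is unknown:

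- one arm's baseline times are recorded 5% slow;
- the log ratio of Week 52 to baseline time is normal, with SD 0.15–0.30 and mean 0–0.1;
- the three criteria (walk, peg test, EDSS) follow a trivariate normal with common correlation r;
- the EDSS criterion is set so that 30% overall are without progression (10.4).

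Per timed test, the chance of progression is p = P(log ratio > ln 1.2) without the shift and q = P(log ratio > ln 1.2 + ln 1.05) with it.

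Example with mean 0.1 and SD 0.20: p = 1 − Φ((0.1823 − 0.1)/0.20) = 0.340 and q = 1 − Φ((0.2311 − 0.1)/0.20) = 0.256. At r = 0.5 the share without progression rises by 1.76 points if one test is affected and 3.74 if both are. Exact enumeration at 33 per arm then gives a false-positive rate of 6.96% or 9.47%. If the shift favours control, power is 76.8% or 71.3%.

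Ranges over the whole grid (SD 0.15, 0.20, 0.25, 0.30; mean 0 and 0.1):

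| r | Timed tests affected | Shift, points | False-positive rate, no true effect, shift favours ECP | Power, 60% v 30%, shift favours control |
|---|---|---|---|---|
| none | no shift | 0 | 5.2% | 81% |
| 0.5 (main) | one | 0.4–1.8 | 5.6–7.0% | 80–77% |
| 0.5 (main) | both | 0.8–3.7 | 6.0–9.5% | 79–71% |
| 0.7 | one | 0.1–0.9 | 5.3–6.1% | 81–79% |
| 0.7 | both | 0.2–2.0 | 5.4–7.2% | 81–76% |
| 0.3 | one | 0.9–2.7 | 6.0–8.1% | 79–74% |
| 0.3 | both | 1.8–5.7 | 7.0–12.6% | 77–65% |
| 0 (upper bound) | one | 1.7–4.3 | 6.9–10.2% | 77–70% |
| 0 (upper bound) | both | 3.5–9.1 | 9.1–19.3% | 72–54% |

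A positive correlation is the main case because 8.1.2 says the mid-range EDSS largely reflects walking; independence is therefore implausible. The calibration to 30% implies that 53–69% of patients progress on EDSS alone in the main case. The documents give no component rates against which to check that.

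**The case against.** **The EDSS is better covered than the timed tests.** This stands in part. An eligibility EDSS should exist before randomisation (inclusion 2). Inclusion 3 even words its rule in terms of the EDSS at baseline, although eligibility is verified at screening. But no section names that score as the endpoint reference, Table 2 and 9.2.3 schedule another EDSS at baseline, and none of this helps the walk or peg test.

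**The timing may be tighter than it looks.** Eligibility needs laboratory results, so randomisation may in practice fall close to baseline. The undefined scoring item at screening could include the MSFC, since 8.1.1 calls it a scoring system. Table 2 shows no MSFC at screening, but it shows no EDSS there either, so that column may be incomplete. These are fair doubts about practice, but they leave the written order unchanged.

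**A release rule may sit in the trial master file.** It may. That file was not available, and Figure 1 is not shown. What is established is that the protocol text has no such rule.

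**The benefit is limited.** The trial stays open-label at every follow-up, the scenario inputs are all assumed, and the main-case effects are modest. All true. The case rests on the visit order and the low cost of correcting it, not on the scenario figures.

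**Conclusion.** The concern holds. Followed as written, the plan lets the reference values of a change-from-baseline primary endpoint be recorded after the arm is known, most clearly for the timed walk and peg test. This is a possibility that the text leaves open, not evidence that bias occurs. Under the main scenario, the error rate moves by about 0.4 to 4.3 percentage points (5.2% to between 5.6% and 9.5%), and power falls by about 1 to 10 points (81% to between 80% and 71%). Those sizes rest on the assumed 5% slowing, spread, drift and correlation. The point should be fixed; it does not undermine the design. Confidence is moderate because the master file was not seen.

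**What to change.** - In Table 2, move the randomisation mark from Screening to Baseline.
- Move the randomisation bullet from 9.2.2 to follow the MSFC and EDSS bullets in 9.2.3, and add: *The IVRS assignment is released only after baseline EDSS and MSFC have been recorded.*
- In 10.2.1, state that baseline means these pre-assignment values.
- Holding the assignment for the MRI and immune bloods is optional, because they enter no primary criterion.
- If the trial master file already withholds the assignment until then, state the rule in 10.1 and align Table 2 and 9.2.2 with it.

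**Cost.** One mark and one bullet are moved and two sentences added; N = 66 and the stated 80% power are unchanged. ECP booking can begin only after the baseline visit, and the IVRS call point may need resetting. The time left for booking depends on which start window applies: 3.1 and 10.1 give 5 days from baseline, while Table 2 and 9.2.3 give 14. That conflict already exists, and the sections must be reconciled in any case. Open-label bias at Week 52 remains.

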9.2.3 Baseline (Week 1)

A baseline visit should be performed and 1st ECP scheduled within 14days.

- Physical examination.
- Interim History
- Vital signs.
- MSFC
- MRI
- EDSS
- Blood for immune parameters (sent to the University of Michigan Neuroimmunology Research Laboratory)
- Collect blood sample for laboratory assessment (Table 1)
- Record concomitant medication.
- Assessment of pre-treatment events (AEs occurring from ICF signed to baseline visit).
- Start ECP within 14 days of baseline as defined in the schedule of assessments

9.2.4 Month 3/Week 12

- At this point patients who are assigned to ECP arm will have been tapered from 3 treatments weekly to two treatments weekly.
- Patients randomized to the ECP arm must receive their first ECP treatment within 14 days of baseline visit.
- Before ECP, on each day of treatment, blood samples will be collected for CBC or other clinical routine testing as needed, and no less that weekly.
- Patients admitted to the corticosteroid arm will receive a treatment once every month as stated above

- The following will also be performed at this time point: Interim history, vital signs, physical exam.
- Blood for immune parameters (sent to the UM Neuroimmunology Research Laboratory)
- MSFC
- EDSS
- Adverse Events
- Concomitant Medications

9.2.5 Month 6/Week 24

At this point patients on ECP will have been tapered to two treatments (on 2 consecutive days) every 2 weeks. If preferred, patients may be given the option of receiving one weekly treatment (as opposed to two treatments on 2 consecutive days) a schedule modification

- Before ECP on each day of treatment blood samples will be collected for the laboratory tests on Table 1 and sent to the University of Michigan Clinical Laboratory
- Patients admitted to the corticosteroid arm will receive a treatment once every month as stated above
- The following will also be performed at this time point:
 - Interim history, vital signs, physical exam.
 - Blood for immune parameters (sent to the UM Neuroimmunology Research Laboratory)
 - MSFC
 - EDSS
 - Adverse Events
 - Concomitant Medications
 - MRI with Gadolinium

9.2.6 Month 9/Week 36

On weeks 37-43, ECP-treated patients transition to one treatment every two weeks and for Patients admitted to the corticosteroid arm will receive a treatment once every month

- Before ECP on each day of treatment blood samples will be collected for the laboratory tests on Table 1 and sent to the University of Michigan laboratory to perform testing as described above.
- Patients admitted to the corticosteroid arm will receive a treatment once every month as stated above
- The following will also be performed at this time point:
 - Interim history, vital signs, physical exam.
 - Blood for immune parameters (sent to the UM Neuroimmunology Research Laboratory)

- MSFC
- EDSS
- Adverse Events
- Concomitant Medications

9.2.7 Week 52 through the End of Study

- From Weeks 44-52, patients will receive one ECP treatment every 4 weeks
- Patients admitted to the corticosteroid arm will receive a treatment once every month
- Before ECP on each day of treatment blood samples will be collected for the tests outlined on Table 1
- The following will also be performed at this time point:
 - Interim history, vital signs, physical exam.
 - Blood for immune parameters (sent to the UM Neuroimmunology Research Laboratory)
 - MSFC(every 3 months through 2 years)
 - EDSS (every 3 months through 2 years)
 - Adverse Events
 - Concomitant Medications
 - MRI with Gadolinium

9.2.8 Early Termination Visit

Patients who withdraw from the study before Week 52 but at the time of a scheduled visit must complete Week 52 assessments. If a patient withdraws between scheduled visits, the patient must come into the clinic to perform the Week 52 assessments. This study does not allow for cross-over between study group to control group or vice-versa while on study.

10. STATISTICAL METHODS

Any deviations from the planned analyses will be described and justified in the final integrated study report.

10.1 Planned Sample Size and Number of Study Centers

It is planned to recruit approximately 66 patients (33 per treatment arm). This is a single center study.

Patients will be randomized on a 1:1 basis to corticosteroids or ECP arm.

Patients randomized to the ECP treatment arm must receive their first treatment within 5 days of the baseline visit.

For the randomization of patients, the investigator will use an Interactive Voice Response System (IVRS). Details can be found in the trial master file. IVRS will assign patients to a treatment group based on the pre-defined randomization list.

10.2 Efficacy Analyses

10.2.1 Analysis of Primary Endpoint

The primary end point is the proportion of subjects with no evidence of disease progression, as defined below, at Week 52. Intent to treat approach will be used. Progression is defined as a minimum change from baseline in one or more of the following parameters:

- 20% or greater increase in the timed 25 foot walk
- 20% or greater increase in the 9 hole peg test
- 1 point or greater increase in EDSS score in subjects with baseline EDSS scores between 3 and 5.5
- 0.5 point or greater increase in EDSS score in subjects with baseline EDSS scores equal to or greater than 6

The proportion of subjects who have not progressed clinically, based on the above criteria, at Week 52 after initiation of study therapy will be compared between treatment groups using the Chi-square test.

The early drop-outs, including patients who withdraw will be considered as non-responders.

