5. PATIENT WITHDRAWAL AND REPLACEMENT

Patients may withdraw from the study at any time without penalty and for any reason without prejudice to his or her future medical care.

Patients must be withdrawn under the following circumstances:

- The patient withdraws consent
- Pregnancy (see Section 8.2.2.9)
- Unacceptable toxicity including patients on corticosteroids who develop psychosis or aseptic necrosis of the femoral head

Patients may be required to withdraw after discussion with the investigator for the following reasons:

- AE(s)
- At the discretion of the investigator
- Violation of eligibility criteria
- Deviation from the treatment plan specified in the protocol (e.g., incorrect administration of the study drug, failure to attend study visits, etc.)
- The treating physician can withdraw the patient from the study at any time and for any medical reason that he/she deems necessary
- The patient has a right to withdraw at any time, for any medical or other reasons.
- Patients who experience a clinical relapse (defined as neurological event characterized by new or worsening symptoms lasting 48 hours after a stable period of at least 30 days and is considered in the judgment of the investigator to be a clinical relapse). Patients who fail therapy will be off study, and further therapy will be at the discretion of the treating neurologist. The study will not cover any form of therapy after the patient is off study.
- Patients who have interval accumulation of T1 or T2 lesions and/ or gadolinium enhancing T1 lesions on the month 6 MRI scan
- In all cases, the reason(s) for withdrawal, and the primary reason, must be recorded on the case report form (CRF) or similar.

Withdrawn patients will be replaced.

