10.4 Determination of Sample Size

Assuming that the proportion of subjects in the corticosteroid treatment who show no evidence of clinical progression at 52 (12 months) is 30%, 66 subjects (33 per treatment arm) provides at least 80% power to detect a treatment difference of 30% (i.e., 60% of the ECP treated subjects will show no evidence of clinical progression at 12 months), based on the normal approximation of the binomial distribution and a one-sided Type I error of 5%.

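### The stated 80% power makes no allowance for withdrawals, which the primary analysis scores as failures; equal withdrawal of 10% to 20% lowers it to about 73% to 66%, or 77% to 75% with replacement

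*Combined protocol and SAP*

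**What the plan says.** Section 10.4 sets the control rate ("Assuming that the proportion of subjects in the corticosteroid treatment who show no evidence of clinical progression at 52 (12 months) is 30" per cent) and the ECP rate ("60% of the ECP treated subjects will show no evidence of clinical progression at 12 months"). It concludes that "66 subjects (33 per treatment arm) provides at least 80% power to detect a treatment difference of 30" percentage points, "based on the normal approximation of the binomial distribution and a one-sided Type I error of 5" per cent. The synopsis gives the same control rate, difference, sample size and power. Neither mentions withdrawal, and the recruitment target in Section 10.1 is the same 66 patients.

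Section 10.2.1 defines progression by timed walk, peg test and EDSS, uses intent to treat with a chi-square test at Week 52, and closes with the rule "The early drop-outs, including patients who withdraw will be considered as non-responders".

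Section 5 lists mandatory withdrawals and then further grounds, introduced by "Patients may be required to withdraw after discussion with the investigator for the following reasons". These include adverse events, deviations from the treatment plan, missed visits, clinical relapse and new lesions on the month 6 MRI. It also says that those who withdraw are replaced. Neither Section 5 nor Section 10 says whether a replaced patient stays in the primary analysis. No expected withdrawal rate appears anywhere.

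**The concern.** As worded, the planning rates describe clinical non-progression. The primary analysis measures something narrower: the proportion who neither progressed nor withdrew. Any patient who would have been progression-free but withdraws moves from success to failure. If both arms lose such patients at the same rate, both proportions shrink, and so does the difference between them.

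Several grounds in Section 5 are not part of the progression definition, so a patient stable on walk, peg test and EDSS can still be scored a failure. Treatment burden also differs. The Section 6.2 schedule comes to about 66 ECP sessions (24 + 16 + 20 + about 6), against about 13 infusions (52 / 4). That makes unequal withdrawal plausible, though it does not establish it.

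At stake is how a null result is read. A reader relying on 80% power could take it as evidence against a 30-point clinical effect that the planned analysis had less power to detect.

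**Working it through.** **Inputs.** Rates of 30% and 60%, 33 per arm and one-sided 5% by normal approximation come from Section 10.4; 1:1 allocation from 10.1; intent to treat and the non-responder rule from 10.2.1; replacement from Section 5. Withdrawal rates w_C (control) and w_E (ECP) are assumptions.

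**Formula.** Power = Φ{[(p_E − p_C) − 1.645·s0] / s1}, where s0 = √[p̄(1−p̄)(1/n_C + 1/n_E)], p̄ is the pooled proportion, and s1 = √[p_C(1−p_C)/n_C + p_E(1−p_E)/n_E].

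**The plan's figure.** With p_C = 0.30, p_E = 0.60 and n = 33: s0 = 0.12247, s1 = 0.11677, and (0.30 − 0.20145)/0.11677 = 0.844. Power is 80.06%. With 32 per arm it is 78.9%, so 33 is the minimum.

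**Withdrawal scored as failure.** If withdrawal is unrelated to outcome, p_C = 0.30(1 − w_C) and p_E = 0.60(1 − w_E). For example, 10% in both arms gives 27% versus 54%: (0.27 − 1.645 × 0.12085)/0.11619 = 0.613, so power is 73.0%.

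**Replacement.** If recruitment continues until 33 per arm complete and everyone randomised is analysed, n = 33/(1 − w), rounded up. At 10% that is 37 per arm: (0.27 − 1.645 × 0.11413)/0.10973 = 0.750, so power is 77.3%.

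| Withdrawal, control / ECP | Analysed rates | Power, 33 per arm | n with replacement | Power with replacement |
|---|---|---|---|---|
| 5% / 5% | 28.5% / 57% | 76.6% | 35 / 35 | 78.8% |
| 10% / 10% | 27% / 54% | 73.0% | 37 / 37 | 77.3% |
| 20% / 20% | 24% / 48% | 65.5% | 42 / 42 | 74.8% |
| 10% / 20% | 27% / 48% | 54.8% | 37 / 42 | 61% |
| 10% / 5% | 27% / 57% | 80.7% | 37 / 35 | 83.7% |
| 15% / 10% | 25.5% / 54% | 77.4% | 39 / 37 | 82.5% |
| 20% / 10% | 24% / 54% | 81.5% | 42 / 37 | 87.3% |

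Exact enumeration of the one-sided test at 33 per arm agrees to about 1 point in the equal cases: 77.7%, 73.9% and 66.1%.

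**Withdrawal related to outcome.** If only would-be progressors withdraw, the analysed rates stay at 30% and 60%, and power at 33 per arm stays at 80.06%. If would-be progressors are three times as likely to withdraw, power at 33 per arm is 76.8% at 10% overall withdrawal and 73.4% at 20%.

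**The case against.** The calculation in Section 10.4 is correct on its own terms, so this is an unstated assumption and not an arithmetic error. Four further points can be made for the plan.

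- **The rates may already be composite.** The synopsis and Section 10.2.1 use nearly the same phrase for the planning rate and for the endpoint, so 30% and 60% could be values for the endpoint as analysed. That reading is open, but nothing states it, and Section 10.4 speaks only of clinical progression.
- **Replacement is planned.** Figures that hold 33 per arm fixed therefore do not describe the whole plan. This stands: at 10% and 20% equal withdrawal, replacement reduces the loss from about 7 and 15 points to about 3 and 5. It does not remove the loss. In the equal-withdrawal cases, 80% is preserved only by dropping replaced patients from the analysis, which contradicts intent to treat and the non-responder rule.
- **Withdrawal may track outcome.** Relapse and new MRI lesions are grounds for withdrawal, and such patients may well have been going to progress. If 5% of non-progressors and 15% of progressors withdraw in each arm, overall withdrawal is 12% control and 9% ECP, and the rates are 28.5% and 57%. With replacement (38 and 37 analysed) power is 81.3%; at 33 per arm it is 76.6%.
- **The direction between arms is unknown.** A reader might infer that any realistic withdrawal takes power below 80%, or that the claim holds only with none. The documents do not support either. They give no rate for either arm, and the table includes unequal cases that stay above 80%. The difference in session burden is a reason to examine heavier ECP withdrawal, not evidence that it will occur.

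**Conclusion.** The concern holds in limited form. The stated power has no reserve and takes no account of a scoring rule that the primary analysis applies. Under equal withdrawal unrelated to outcome, power is below the stated figure with or without replacement: by about 3 to 15 points at 5% to 20% withdrawal with 33 per arm analysed, and by about 1 to 5 points with replacement and full intent to treat. The most damaging case examined is 10% control and 20% ECP, at 55%, or 61% with replacement.

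The size rests on assumed withdrawal rates, on how withdrawal relates to outcome and arm, and on reading 30% and 60% as clinical rates. What can be said firmly is that the plan does not show that its own analysis rule delivers at least 80%.

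**What to change.** In Section 10.4 and the synopsis:

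1. Restate power under the Section 10.2.1 non-responder rule for a stated range of withdrawal by arm, with both equal and unequal cases. Alternatively, state that 30% and 60% already count withdrawals as failures. That choice needs its own support: at 10% equal withdrawal unrelated to outcome it implies clinical rates of 0.30/0.90 = 33.3% and 0.60/0.90 = 66.7%.
2. State that replaced patients stay in the intent-to-treat analysis as failures, and use the power figures that match. With 10% and 20% equal withdrawal these are 77% and 75%, not 73% and 66%.

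The cost is a few sentences and a less favourable stated power. No patients are needed beyond those the replacement rule already brings in, and the test, endpoint and visits do not change.
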